- IV. the purpose of the research and the importance of recording their 'usual' food intake will be explained to the participants to minimise reporting bias. Participants will be advised that they will not be judged on their diet, and they should avoid making dietary changes during the recording period.
- V. participants will also be able to contact the CI for additional app support by phone or email.
- VI. A date will be agreed with the participant when they will commence recording their food intake. Participants will receive a reminder notification from MyFood24 to complete a food diary for each day. Participants completing a paper diary will receive a text message reminder from CI during the monitoring period in week 1 and 2. MyFood24 dietary target notifications will be turned off to minimise this influencing their food intake e.g., modifying it in response. The participant will be provided with information on how to use the app and links to 'YouTube' videos in their study information booklet (see appendix).
- VII. At the end of their participation in the study the participants will be advised to delete the MyFood24 app.

Physical Activity Monitoring

Accelerometery will be used to measure physical activity over 14 days. Physical activity is defined as any bodily movement produced by skeletal muscles resulting in energy expenditure (67). Sedentary behaviour is defined as sitting, reclining, or lying postures, excluding sleep, with energy expenditure of ≤1.5 metabolic equivalents (METs)(68). Accelerometers are electronic devices capable of continuously recording changes (accelerations) in

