movement. Triaxial accelerometers measure movement in three axes (directions); X (left to right), Y (forward and backward), and Z (up and down). Data can be analysed to provide an estimate of time spent in different frequencies, intensities, and durations of physical activity. Seven days wear (≥10 waking hours/day) is usually considered a sufficient time to gather data on habitual physical activity patterns (69). Longer wear periods are recommended where adult populations may demonstrate higher variability in levels of physical activity week to week (70). In this study, the measurement time frame will therefore be 14 days of continuous wear (including overnight), to ensure habitual levels of physical activity are reliably captured. Overnight wear also helps to increase compliance, and provides important data on sleep (quantity, efficiency), which is important to understand when investigating physical activity (69).

Participants will be provided with an ActiGraph wGT3X-BT monitor (Actigraph, Pensacola, Florida, USA), either in person at visit 1 or by post from the Chief Investigator following this visit. They will be instructed to wear this on their non dominant wrist for 14 days. The participant will be advised to wear the monitor for at least 10 hours a day up to 24 hours per day. They will be advised that the monitor is not waterproof and they should not wear it whilst swimming, taking a bath or a shower. A date, time and location for study visit 2 will be arranged with the participant (2 weeks' time from study visit 1). The participants GP will be informed of their participation in the study by letter.

5.1.2 Study Visit 2- Verification of Food Diary and Return of Physical Activity Monitor (week 3-7)

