5.1.4 Data Analysis

The quantitative and qualitative data will be analysed separately and integrated;

Descriptive statistics will be performed on all quantitative outcomes using SPSS vs 27 (75)

Quantitative Data Analysis

The self-reported food intake diary will be analysed using myfood24® nutritional analysis software(76). The food diary and nutrient intake data will be generated from MyFood24® (see appendix) in a Comma Separated Values (CVS) output file and saved on a University of Birmingham password protected server (see Data Management Plan (DMP)). Participants who complete less than 3 days food records will be excluded from the dietary data analysis, as it is unlikely to be a true representation of their habitual food intake and will not be approached for interview

Daily mean nutrient intakes will be calculated for each participant, across the number of days completed food diary data. For macronutrients and free sugars, both total and total food energy-adjusted values (per 1000kcal) will be reported employing Atwater factors(77). Fibre will be quantified using the Association of Official Analytical Chemists (AOAC) method. Nutrient intake data will be compared to Dietary Reference Values for food and Nutrients in the UK(78), Scientific Advisory Committee on Nutrition Recommendations(79-81), European Cystic Fibrosis Nutrition Guidelines(82);

In addition, percentage distribution of nutrients (energy, fat, carbohydrate, total sugar, protein, fibre, calcium) per meal (breakfast, lunch, evening dinner, snacks, drinks) will be summarised and the top 5 foods that contribute to intake of energy, fat, carbohydrate, total sugar, protein, fibre, and calcium will be tabulated.

Physical Activity Data

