Participants accelerometery data will be downloaded, analysed and stored using Actilife® software (version 6.2)(72). This software will be accessed via and the data will be stored on a University of Birmingham password protected computer server. Once the data has been downloaded the participant data will be cleared from the device. The physical activity data will be summarised and exported as a pdf file and saved on a University Hospitals Birmingham password protected computer server A summary of this data will be entered into the participant Case Report Form. Non-wear time will be determined by Actilife® software. Participants with < 10 hours valid wear time per day, for <4 days, will be excluded from the analysis. The amount of valid wear time will be used as a co-variate in any statistical analysis, to account for variability between participants.

Accelerometer cut-points will be used to compute average total daily sedentary time (SED), light-intensity physical activity (LPA), and moderate-to-vigorous-intensity physical activity (MVPA) (83-86).

Qualitative Data Analysis

The audio-recording and transcription will be imported into NVivo 12(87). NVivo 12 will be used to organise, and chart the focus group interview data.

The framework approach will be used to analyse the data (52, 88). This method has been chosen as it is a systematic process for organising, reducing, and interpreting qualitative data. It guides a process of thematic analysis with the development of an analytic framework and charting matrix from the coding and categorising of interview data to aid the comparison across the data set so that relationships, and patterns can be developed into key themes. An advantage of this method is the inclusion of participant accounts in the matrix ensure that individual descriptions and interpretations are not lost in the analysis.

The following process of the framework approach will be used to analyse the data;

i. Transcription

Following each interview, JB will check the transcription for errors by listening back to the audio-recording and reading the transcripts simultaneously. Corrections will be made to ensure an accurate verbatim transcription for analysis.

ii. Familiarisation with the interview

JB will listen back/view to the audio recording and read and re-read the transcript to familiarise with the data thoroughly. Initial analytical thoughts on the key study objectives, relevant issues that emerge and impressions will be noted.

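### The activity monitor is meant to be worn day and night for 14 days, but participants are given a floor of 10 hours a day, so the reported daily totals partly reflect hours worn

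*Protocol*

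**What the plan says.** All references are to the Protocol.

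- **Design (section 5.1.1, Physical Activity Monitoring).** After noting that longer wear suits populations whose activity varies from week to week, the section states: "the measurement time frame will therefore be 14 days of continuous wear (including overnight), to ensure habitual levels of physical activity are reliably captured". It adds a further reason for wear at night: "Overnight wear also helps to increase compliance, and provides important data on sleep (quantity, efficiency").
- **Advice to participants (same section, next paragraph).** They are to wear the device on the non-dominant wrist for 14 days, and then: "The participant will be advised to wear the monitor for at least 10 hours a day up to 24 hours per day". Removal for swimming and washing is covered separately.
- **Benchmark (same section).** "Seven days wear (≥10 waking hours/day) is usually considered a sufficient time to gather data on habitual physical activity patterns". This counts waking hours; the advice to participants does not say so.
- **Outcomes (section 5.1.4, Physical Activity Data).** Cut-points are used to "compute average total daily sedentary time (SED), light-intensity physical activity (LPA), and moderate-to-vigorous-intensity physical activity (MVPA"). These are absolute times.
- **Handling of unequal wear (same place).** ActiLife identifies non-wear. The exclusion rule appears to keep anyone with 10 valid hours on 4 days. Valid wear time is to be a covariate in any statistical analysis.
- **Analysis (section 5.1.4).** "Descriptive statistics will be performed on all quantitative outcomes using SPSS" version 27. A descriptive summary then goes into the joint display.
- **Interview prompts (section 5.1.2).** Each participant's activity data are turned into a visual summary for discussion at interview.

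**The concern.** Two adjacent paragraphs ask for different things. Someone who takes the monitor off every night, or for part of every evening, does what was asked but does not supply the record that the design is built on. Since sleeping hours are not ruled out of the 10, a participant could even reach the floor with fewer than 10 waking hours.

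This matters because the outcomes are totals per day. Two people with identical behaviour get different totals if one wears the monitor longer. The exclusion rule does not separate them, so their totals are averaged together.

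Objective ii (section 4.1) is to characterise activity patterns and assess activity level. The same totals feed the group summary, the joint display and the personal prompts. A participant could be asked at interview to explain a figure that partly reflects when the device was off.

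**Working it through.** The protocol gives no figure to reproduce here. The check sets the stated hours side by side and then illustrates how a daily total depends on wear.

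**1. Hours implied by the protocol**

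- Planned frame: 14 × 24 = 336 h (an upper bound, since washing and swimming require removal).
- Least wear that follows the advice: 14 × 10 = 140 h; 140/336 = 41.7% of the frame.
- Least wear that stays in the analysis, reading the exclusion rule as 10 h on 4 days: 4 × 10 = 40 h; 40/336 = 11.9%.

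**2. Dependence of a daily total on wear**

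Recorded time = share of waking wear spent in the behaviour × waking hours worn. Assumptions, none from the protocol: a 16-hour waking day; a sedentary share of 60% (range 50% to 70%); the same share in worn and unworn hours.

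| Waking hours worn | Waking time unobserved | Sedentary h/day at 50% | at 60% | at 70% |
|---|---|---|---|---|
| 10 | 6/16 = 37.5% | 5.0 | 6.0 | 7.0 |
| 13 | 3/16 = 18.75% | 6.5 | 7.8 | 9.1 |
| 16 | 0% | 8.0 | 9.6 | 11.2 |

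Whatever the share, the full-day total is 16/10 = 1.6 times the 10-hour total for the same behaviour. At 60% the gap is 9.6 − 6.0 = 3.6 h/day (3.0 at 50%, 4.2 at 70%).

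**3. Group mean**

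If a fraction f of participants wear the monitor for 10 waking hours and the rest for 16, then at a 60% share the mean falls by f × 3.6 h/day:

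- f = 0.25: 0.9 h
- f = 0.50: 1.8 h
- f = 0.75: 2.7 h

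If nobody wears it near the floor, the fall is close to zero. The protocol gives no basis for choosing f.

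**4. Does the covariate remove this?**

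A covariate acts through a model. The outputs that section 5.1.4 describes are descriptive summaries, and the prompt in section 5.1.2 is one person's own data. Neither contains a term that could carry wear time.

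**The case against.** **The strongest reply is that the protocol foresees unequal wear.** It sets a validity threshold, has software detect non-wear and names wear time as a covariate. It plans descriptive statistics but does not say that these are the only analyses, so a model may yet exist. How to normalise for wear is often left to an analysis plan. Much of this is fair, and one should not infer that the covariate has no use at all. What stands against it is narrower: it cannot adjust the descriptive means or the individual prompts. Nor can an analysis plan restore hours that were never recorded, because the wear instruction is a data-collection rule.

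**Ten hours is a floor, and 24 hours is named in the same sentence.** That is right. A reader might infer that participants are told 10 hours is enough, but the text says only that it is the least they should do. Many may wear the device far longer. The participant information is a separate appendix that is not shown, and it may be clearer.

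**Sleep.** A reader might infer that a 10-hour wearer gives no sleep data. This does not follow, because the 10 hours may include the night. Sleep also appears in no objective or outcome (sections 4.1 and 4.2). Nor do the documents support a claim that sleep would be scored as sedentary: section 5.1.1 defines "Sedentary behaviour is defined as sitting, reclining, or lying postures, excluding sleep".

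**Shares of wear time are not a cure.** This too is correct. If unworn hours differ in behaviour from worn hours, shares are biased as well. Absolute minutes are also needed for comparison with the 150 minutes a week mentioned in section 1. Shares should therefore supplement minutes, not replace them.

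**Low stakes.** Priority goes to the qualitative data (section 3), no sample size rests on these totals, and participants can say at interview when the device was off. This limits the consequence but does not remove it, since objective ii is itself quantitative.

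**Conclusion.** The point holds in a limited form. The planned frame and the advice in section 5.1.1 do not agree, and the advice omits the waking-hours qualifier of the benchmark cited just above it. Because section 5.1.4 reports absolute daily totals, those totals partly reflect hours worn, in the group description and in the individual prompts.

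The mismatch itself rests on no assumption: 140 h satisfies the advice, against a frame of up to 336 h. The size of its effect does rest on assumptions. The figures of 37.5% unobserved and 3.6 h/day describe one hypothetical participant at exactly 10 waking hours of a 16-hour day, the second also with a 60% sedentary share. A reader might take them as the bias expected in the study. The documents do not support that, because nothing shows how many participants would wear the device near the floor or at what times they would remove it.

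The change is worth making because it is cheap and affects what is recorded under a stated objective.

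**What to change.** 1. **Section 5.1.1.** Bring the participant instruction into line with the planned frame: wear day and night for 14 days, removing the monitor only for bathing, showering and swimming. Make the same change in the participant information if it carries the same advice.
2. **Threshold.** Keep 10 hours, specified as waking hours, only as the analyst's test of a valid day in section 5.1.4.
3. **Section 5.1.4.** Report wear time, and report sedentary, light and moderate-to-vigorous time as a share of waking wear time alongside total minutes. Show the same in the interview prompts and the joint display, so that a low total can be read against the hours behind it.

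**Cost.** This needs one sentence in the protocol, possibly one in the participant information, and a few derived columns. Wear burden rises somewhat. Section 10.4 records that the patient group accepted 14 days of monitoring but says nothing specific about nights, and section 10.1 notes that some may feel self-conscious wearing the device; acceptability of overnight wear should not be presumed. For participants already measured, shares and wear time make the totals easier to interpret but do not recover unobserved hours.

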Study visit 2 will take place in a mutually convenient time; face to face in a private clinic room at WMACFC, SACFC, NWMCFC, WCFC or in the participants home, alternatively remotely by phone or via a videoconferencing platform using a MS Teams/Zoom© University of Birmingham account via the University of Birmingham secure server. If via videoconferencing participants will be sent an invitation link to the virtual meeting room by email. The link will have a passcode which will only be available to the participant. The option of interviewing via video has been included to facilitate interviews with participants located a considerable distance from their CF centre and throughout the UK. Video interviews will also give more flexibility for interview date and time for those participants who are not available during normal working hours.

If Visit 2 takes place at the participants home, the CI will adhere to University of Birmingham Health and Safety Guidance on Home Visits . The visit will be risk assessed.

i. Food diary Verification

JB will view participants food diary data via the MyFood24 web-based platform and check with the participant that that the correct food type has been entered, portion sizes are accurate and probe if any food items have not been recorded using a checklist (see appendix) and pictorial portion size food Atlas(71). Incorrect or absent entries will be amended by CI in agreement with the participant.

ii. Physical Activity Monitor

The physical activity monitor will be returned by the participant. If study visit 2 takes place virtually, they will be asked to either; 1) return the physical activity monitor by post in a pre-paid envelope to the CI/PI at WMACFC/SACFC/NWMCFC/WCFC, 2) JB will arrange to collect from the participants home, or 3) a member of the CF Team will arrange to collect the monitor from the participants home during a scheduled clinical home visit (adhering to university home visit or local lone worker policies). Once the physical activity monitor has been returned by the participant, they will be sent a £10 retail voucher. All participants who take part in the study will be invited to join the co-design team for the next phase of the study by letter which will be sent with the retail voucher.

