The participants physical activity data recorded on the ActiGraph wGT3X-BT (Actigraph, Pensacola, Florida), USA) will be downloaded via the Actilife software (using Actilife® software (version 6.2)(72) on a University Hospitals Birmingham password protected computer as soon as possible once the device being returned, not exceeding 2 weeks after being received by the Chief Investigator. Once the data has been downloaded the participant data will be deleted from the device. The device will then be cleaned using disinfectant wipes. Data is linked by participant ID only.

Each participants food diary, eating pattern and physical activity data will be summarised in a visual format to use as a data prompt to stimulate discussion during the semi-structured interviews. A copy of the food diary and physical activity summaries will be entered in the paper and electronic CRF. These will be saved on a University of Birmingham password protected server (see Data Management Plan)

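### Participants take the monitor off to swim, and the protocol body describes no record or use of exercise done without it, so a swimmer's MVPA is understated

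*Protocol*

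**What the plan says.** Section 5.1.1 (Physical Activity Monitoring) starts from a broad definition: "Physical activity is defined as any bodily movement produced by skeletal muscles resulting in energy expenditure". It sets a 14-day window "to ensure habitual levels of physical activity are reliably captured". On the device it says: "They will be instructed to wear this on their non dominant wrist for 14 days". Because the device does not tolerate water, participants are also advised that "they should not wear it whilst swimming, taking a bath or a shower".

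Section 5.1.2 (Study Visit 2) treats the two data sources differently. For diet, the chief investigator goes through the diary with the participant, probes for unrecorded items with a checklist, and corrects the entries. For activity, the step is: "The physical activity monitor will be returned by the participant". The rest of that item covers return logistics, the voucher, download and cleaning. The schedule of procedures in Appendix 2 shows the same split, with the diary verified and the monitor returned.

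Section 5.1.2 also says that each person's diet and activity data "will be summarised in a visual format to use as a data prompt to stimulate discussion" in the interview.

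Section 5.1.4 (Physical Activity Data) says: "Non-wear time will be determined by Actilife® software". It names no algorithm and no minimum length for a non-wear period. Average daily sedentary, light and moderate-to-vigorous time come from cut-points, and valid wear time is a covariate in any statistical analysis. No step adds activity done with the monitor off.

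**The concern.** Swimming falls within the protocol's own definition of physical activity, yet participants are instructed to do it without the monitor. The gap comes from the design, not from poor compliance. For anyone who swims at moderate or higher intensity, the MVPA error runs one way: the device can miss those minutes but cannot add any.

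Two uses of the data are affected. One is the quantitative description of activity pattern and level (objective ii in section 4.1). The other is the individual summary used as the interview prompt. Section 3 gives priority to the qualitative data, and section 5.1.4 plans a joint display that sets participants' perceptions against the quantitative results. A regular swimmer who rightly describes being active could be shown a low figure, and the difference could be read as a gap between perception and behaviour when it is a gap in measurement.

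This is a data-collection matter. If the sessions are not asked about during or soon after the monitoring period, no later analysis can restore them.

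**Working it through.** The protocol states no figure on this point: no swimming rate, no expected MVPA and no calculated sample size. There is nothing to reproduce, so the check is a reading of the data path followed by arithmetic on assumed rates.

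**Do the existing rules repair the gap?**

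- *Valid-data rule (section 5.1.4).* The rule uses 10 hours a day and 4 days. A swim of 30 to 60 minutes in a day of otherwise near-continuous wear leaves that day valid, so it enters the average without the swim.
- *Wear-time covariate (section 5.1.4).* It adjusts for how long the device was worn, not for what was done without it. Take an assumed day with a 60-minute swim, 20 minutes of other MVPA and 16 hours of intended wear. True MVPA, counting the whole swim, is 20 + 60 = 80 minutes, and recorded MVPA is 20. Proportional scaling for wear gives 20 × 16/15 = 21.3 minutes. That recovers (21.3 − 20)/60, or about 2% of the swim.

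**Size for one swimmer.** Loss per day = weekly swim minutes / 7, counting every pool minute as MVPA.

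| Assumed swimming, min/week | Loss, min/day | Loss over 14 days, min |
|---|---|---|
| 30 | 30/7 = 4.3 | 60 |
| 60 | 60/7 = 8.6 | 120 |
| 90 | 90/7 = 12.9 | 180 |

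**Size for the group.** Loss in the mean = share who swim × weekly swim minutes / 7.

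| Assumed share who swim | 30 min/week | 60 min/week | 90 min/week |
|---|---|---|---|
| 10% | 0.4 min/day | 0.9 min/day | 1.3 min/day |
| 20% | 0.9 min/day | 1.7 min/day | 2.6 min/day |

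**How many interview prompts.** Section 5.1.3 plans 20 to 30 interviews. If interviewees swim at the same assumed rates, 20 × 10% = 2 to 30 × 20% = 6 prompts would be affected.

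**Sedentary time.** If the software scores a removal as sedentary, sedentary time is overstated by up to the same 4.3 to 12.9 minutes a day for that swimmer. If it scores the removal as non-wear, sedentary time is not inflated. MVPA is missed either way.

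**The case against.** Several points on the other side carry weight.

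- *A record may exist elsewhere.* The visit 2 checklist, the case report form and the participant information on activity monitoring are appendices that were not available. A removal log could sit in any of them. A reader might infer that the study records nothing about device-off exercise; the documents do not show that. They show only that the protocol body mentions no such record and uses none. This stands as a limit on the point.
- *The mechanism is not fixed.* A reader might infer that swimming is always processed as non-wear. Section 5.1.4 names no algorithm, so a short removal could be scored as sedentary. This also stands, and it means that sedentary time may be affected too.
- *The measure is device-based by choice.* Objective ii refers to accelerometry, and missing water activity is a known limit of a monitor that is not waterproof. That is a good reason to keep device MVPA as the main figure. It is not a reason to leave the known gap unmeasured.
- *The size rests on assumptions.* The rates are assumed, and not every pool minute is moderate or harder, so the losses are upper values for those rates. It is tempting to express the loss as a share of the 150 minutes a week in section 1. That figure is background advice from before modulator therapy, and the protocol does not plan to classify participants against it.
- *The interview can correct itself.* The summary is a stimulus used with open questions and probes, and a swimmer can say what is missing. This softens the harm to the prompt but leaves the quantitative summary uncorrected.

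**Conclusion.** The point holds in a limited form. On the protocol body as written, moderate or harder swimming is missing from MVPA, and neither the valid-data rule nor the wear-time covariate restores it. Under the assumed rates, a swimmer loses about 4 to 13 minutes a day (30 to 90 minutes of swimming a week), and the group mean loses about 0.4 to 2.6 minutes a day (10 to 20% swimming). Both ranges count all pool time as MVPA and are upper values for those rates.

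The group effect is small. A reader might infer that the study's overall activity results are seriously biased; the arithmetic does not support that. The effect can be material for an individual swimmer's interview prompt, and that is the main reason to act. This is a modest, worthwhile improvement and does not threaten the study.

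**What to change.** Add one item to visit 2, or to a short removal log kept during the 14 days: the date, minutes and perceived intensity of swimming or other exercise done with the monitor off. Then:

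- keep device MVPA as the main figure;
- report a sensitivity figure that adds the sessions the participant rates as moderate or harder;
- make sure those periods are not counted as sedentary time;
- mark the sessions on the individual visual summary before the interview.

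If a log already exists in the appendices, the change reduces to linking it to the analysis and to the prompt.

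The cost is a brief question at an existing visit or a short log, one line on the case report form, and some work on each affected summary. The change also needs a protocol amendment under section 10.2.2. The added minutes and intensities are self-reported and, if asked only at visit 2, recalled after the monitoring period. They should therefore stay out of the main figure, and a log kept during the 14 days would depend less on recall.
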